3. STUDY DESIGN

3.1 DESCRIPTION OF STUDY

3.1.1 Overview of Study Design

This is a Phase 2b (GV29216), randomized, double-blind, placebo-controlled study designed to assess the safety and clinical activity of a single IV dose of 3600 mg MHAA4549A or a single IV dose of 8400 mg MHAA4549A in hospitalized patients with severe influenza A in combination with oseltamivir versus a comparator arm of placebo with oseltamivir. *A Sponsor-approved influenza test that includes influenza antigen test or influenza polymerase chain reaction (PCR) test must be used to diagnose influenza A infection for study eligibility.* This study is planned to take place in approximately 170 study centers globally.

Initially, GV29216 targeted enrollment into two treatment groups: a single IV dose of 3600 mg of MHAA4549A with oseltamivir or a single IV dose of placebo with oseltamivir.

[figure not shown]
In this version of the protocol, patients will be randomized 1:1:1 into three treatment groups: a single IV dose of 3600 mg of MHAA4549A with oseltamivir, a single IV dose of 8400 mg of MHAA4549A with oseltamivir, or a single IV dose of placebo with oseltamivir. *Patients will be stratified by country, PPV versus supplemental O₂ at randomization, and suspected or confirmed bacterial pneumonia versus no bacterial*

pneumonia based on the status at randomization. All patients must begin study drug infusion within 48 hours of hospital admission. In addition, all patients will receive oseltamivir as standard therapy for a minimum of 5 days (10 doses) starting no later than 12 hours after completion of study drug administration. Oseltamivir treatment for longer than 5 days is permitted based on local investigator discretion.

Hospitalized patients with an O₂ or PPV requirement will be evaluated for influenza A infection. Enrollment in this study requires ongoing treatment within 24 hours of hospital admission with one of the following:

- any PPV or
- any supplemental O₂ to maintain oxygen saturation (SpO₂) > 92% ([Section 3.3.2](#))

Patients on PPV should not exceed *approximately* 45% of the total patients enrolled in the study.

[figure not shown]

Safety evaluations will also be provided by an IMC and SOC, as defined in the IMC and SOC agreement (see [Section 3.1.2](#)). If after review of available study data, the IMC and SOC conclude that there is a significant toxicity or worsening disease associated with MHAA4549A, they may recommend stopping further enrollment in the study.

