4.2 METHOD OF TREATMENT ASSIGNMENT AND BLINDING

The randomization of patients will be managed by a central Interactive Voice and Web Response System (IxRS) through use of a dynamic hierarchical algorithm which includes a random component. The treatment assignments will be unblinded to selected Sponsor personnel to facilitate ongoing monitoring of safety and tolerability, including members of the IMC and SOC.

All patients will be randomly assigned to receive 3600 mg MHAA4549A, 8400 mg MHAA4549A, or placebo at a 1:1:1 ratio stratified by country, whether patient is on PPV versus supplemental O₂ at randomization, and whether the patient has suspected or

confirmed bacterial pneumonia vs no bacterial pneumonia at randomization. Initially GV29216 randomly assigned patients to receive either 3600 mg MHAA4549A, or placebo at a 1:1 ratio. The updated randomization scheme takes into account the numbers already allocated to these two arms and strata prior to allocating to the three arm design so that by the end of the study there will be an approximate 1:1:1 allocation between the three arms.

All patients will receive oseltamivir (as described in [Table 2](#)) for a minimum of 5 days. Treatment for longer than 5 days is permitted based on local investigator discretion.

Unblinded personnel (i.e., unblinded site pharmacist or other designated, qualified unblinded study personnel) at each study site will prepare the IV infusions of study drug, as described in [Section 4.3.3](#). The Sponsor will provide masking bags and blinded study personnel will administer the study drug. The other parties who are involved in the conduct of the study (i.e., patients and blinded site personnel) will remain blinded to patient-specific treatment assignments until the final database lock after the completion of the study.

Bioanalytical laboratory personnel responsible for performing PK assays will be unblinded to patients' treatment assignments to identify appropriate PK samples to be analyzed. Samples from patients assigned to the comparator arm will not be analyzed except by request (e.g., to evaluate a possible error in study drug administration).

While PK samples must be collected from patients assigned to the comparator arm to maintain the blinding of treatment assignment, PK assay results for these patients are generally not needed for the safe conduct or proper interpretation of this trial.

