4.6.9 Oxygen Saturation Measurements

To ensure that the respiratory status is well recorded, the following daily measurements will be performed. *All* patients will have their SpO₂ and corresponding respiratory

assessments recorded daily in the morning between 6:00 a.m. and 12:00 noon local time. *Unless clinically contraindicated**, patients on low flow O₂ will have a daily trial of their SpO₂ while on and off the supplementation, as outlined in [Appendix 2](#), and both values will be recorded. If a patient is clinically able to be removed from oxygen outside the time window above (6:00 a.m. to 12:00 noon), the trial-off data should be recorded as an unscheduled visit.

If the patient is on oxygen supplementation, SpO₂ measured by pulse oximetry and the corresponding respiratory assessments (e.g., FiO₂, flow rate) will be recorded. If the patient is on PPV, partial pressure of arterial O₂ (PaO₂) and the corresponding respiratory assessments (e.g., FiO₂, ventilator mode, ventilator respiratory rate, positive end expiratory pressure) will be recorded. If clinically appropriate (i.e., the patient is on non-invasive PPV), the conversion table in [Appendix 11](#) may be used for PaO₂.

**If a patient has an SpO₂ <95% while on oxygen supplementation, he/she shall be considered to be “clinically contraindicated” from requiring a trial off oxygen; however, corresponding respiratory assessments should be recorded.*

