6.1 DETERMINATION OF SAMPLE SIZE

The purpose of this study is estimation of the effect size and hypothesis generation regarding the effect of MHAA4549A on the time to normalization of respiratory function relative to the standard of care rather than hypothesis testing. Point and interval estimates will be obtained. Approximately 330 patients will be enrolled. It is assumed that the median time to normalization of respiratory function in the control arm is 5 days. This sample size (approximately 110 patients per arm) provides 71% power to detect a

treatment difference of 1 day for the primary endpoint in both MHAA4549A arms assuming a 2-sided alpha of 0.2 and no difference in efficacy between the two active arms. If the 3600-mg dose shows a treatment difference of 1 day and the 8400-mg dose shows a treatment difference of 1.5 days or more then this sample size provides > 86% power assuming a 2-sided alpha of 0.2.

Operating characteristics (power) under other possible assumptions for 2-sided alpha of 0.2 and true differences of 0.5 to 2 days are provided in [Table 7](#).

Table 7 Operating Characteristics for Proposed Study Design for Several Possible True Underlying Median Values

	True Underlying Median for MHAA4549A							
	3600	8400	3600	8400	3600	8400	3600	8400
	mg	mg	mg	mg	mg	mg	mg	mg
	4 days	4 days	4 days	3.5 days	4 days	3 days	4.5 days	4 days
Hazard Ratio	0.8	0.8	0.8	0.7	0.8	0.6	0.9	0.8
Power of log-rank test ^a	71.4%		86.6%		98.8%		56.2%	

Note: Operating characteristics are based on the following assumptions: 330 evaluable patients, event times are exponentially distributed, median time to normalization of respiratory function in the control arm is 5 days, and patients are followed for 60 days.

^a Two-sided $\alpha = 0.20$.

It should be noted that the study is underpowered for detection of minimally clinically meaningful differences at a 2-sided alpha of 0.05 such as a true hazard ratio of 0.80 in both MHAA4549A arms.

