6.4 EFFICACY ANALYSES

The primary and secondary efficacy analyses will include all randomized patients who are confirmed to be influenza A infected, with patients grouped according to the treatment assigned at randomization.

Time to event data will be *analyzed* using Kaplan-Meier methodology and stratified Cox proportional hazards models and will be summarized using n, median when estimable, hazard ratios, and 95% confidence intervals. Patients who are lost to follow-up (while event free) will be censored at the time that they are last known to be event free.

The ordinal outcomes will be analyzed using a proportional odds model. To supplement the overall summary odds ratio, separate odds ratios will be estimated for each dichotomized definition of improvement that can be formulated from the components of the ordinal outcome. A test for the proportionality assumption will also be made. Patients discharged from the hospital to a rehabilitation facility will be included in category 5. Patients discharged from the hospital to a nursing home will also be included in category 5, unless the patient lived in a nursing home prior to admission to the hospital, in which case the patient will be characterized based on resumption of normal activities.

Estimation of the treatment difference of proportions and *the corresponding* 95% confidence intervals will be calculated using stratum-adjusted Mantel-Haenszel methodology (Koch et al. 1989). For continuous endpoints, Analysis of Covariance methods (after appropriate transformation of data) will be used to estimate treatment differences and 95% confidence intervals.

Other than censoring in the time to event analyses, no other imputation for missing data will be performed.

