6.4.1 Primary Efficacy Endpoint

- Median time to normalization of respiratory function.

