Appendix 1a Schedule of *Activities*

Notes: Unless otherwise indicated, **all assessments on Day 1 should be performed prior to study drug administration**; x's within parentheses, i.e., (x), indicate optional assessments. Please refer to Follow-up Period table for visits to be completed after patient is discharged from hospital prior to Day 60. Any screening assessments completed prior to consent as standard of care do not need to be repeated if done within the screening period. If a patient is unable to be present at the site for a follow-up visit, a telephone visit is *encouraged*.

Hospitalized Days (only to be completed while patients are hospitalized)																						
	D -2,-1	D1 (Randomization)	D2	D3	D4	D5	D6	D7	D8	D9	D10	D11-13	D14	D15-19	D20	D21-24	D25	D26-29	D30	Hospital Discharge ^a	D60 Study Completion or Early Discontinuation while hospitalized	Unscheduled
Informed consent ^b	x																					
Sponsor-approved influenza test ^c	x																					
Inclusion/exclusion criteria	x																					
Medical history and demographic	x																					

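### The stratified Cox model for the primary endpoint leaves out the pre-dose oxygen requirement already being collected; if that requirement is prognostic within strata, the hazard ratio is attenuated and power is lost

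*Combined protocol and SAP*

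**What the plan says.** Section 6.4 analyzes time-to-event endpoints by Kaplan-Meier and "stratified Cox proportional hazards models and will be summarized using n, median when estimable, hazard ratios, and 95% confidence intervals". It does not list the strata and names no covariate for these models. For continuous endpoints the same section plans analysis of covariance. Section 6.4.1 lists the primary endpoint as "Median time to normalization of respiratory function".

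Section 4.2 allocates patients "at a 1:1:1 ratio stratified by country, whether patient is on" PPV or supplemental O₂, and by suspected or confirmed bacterial pneumonia. Section 3.1.1 gives the same three factors.

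Section 4.6.9 states that all "patients will have their SpO₂ and corresponding respiratory" assessments recorded each morning. FiO₂ and flow rate are the examples given for patients on supplementation; PaO₂, FiO₂ and ventilator settings are those for patients on PPV. Appendix 1a schedules the respiratory assessment at screening and on Day 1, and states that, unless otherwise indicated, "all assessments on Day 1 should be performed prior to study drug administration". Section 6.3 defines baseline as the last value before study drug.

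On size, Section 6.1 says: "This sample size (approximately 110 patients per arm) provides 71% power to detect a" one-day difference in both active arms, "assuming a 2-sided alpha of 0.2 and no difference in efficacy between the two active arms".

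**The concern.** The primary outcome is the time until a patient no longer needs oxygen, so its obvious baseline predictor is how much oxygen the patient needs before dosing. The randomization strata capture this only as PPV or not. The protocol itself treats a move from low flow (2–6 L/min) to high flow (above 6 L/min) as clinical failure (Section 3.3.3), yet at baseline both groups share the supplemental-O₂ stratum. PPV is capped at about 45% of enrolment, so the supplemental-O₂ stratum is expected to hold most of the patients.

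When a prognostic baseline variable is left out of a Cox model, the estimated hazard ratio moves toward 1 relative to the ratio conditional on that variable, and the test loses power. Section 6.1 already plans at a two-sided alpha of 0.2 and says the study is underpowered at 0.05 for a hazard ratio of 0.80. Recovering power from data already on the case report form would therefore be useful.

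**Working it through.** **Inputs from Section 6.1 and Table 7.** Control median 5 days, active median 4 days, 330 evaluable patients (110 per arm, so 110 v 220 pooled), exponential times, 60 days of follow-up, two-sided alpha 0.20 (z = 1.2816). Nearly all patients have the event by day 60, so events ≈ 330. Stated power is 71.4%.

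**Reproducing the stated figure.** Pooled active versus placebo, Freedman's formula, event-rate ratio 5/4 = 1.25, allocation 2:1:

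- z = √(330 × 2) × (1.25 − 1) / (1 + 2 × 1.25) = 25.69 × 0.25 / 3.5 = 1.835
- power = Φ(1.835 − 1.2816) = Φ(0.553) = 71.0%

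Simulation of the pooled log-rank test gives 72.9% and Schoenfeld's formula 73.5%. The first column of Table 7 is therefore consistent with a pooled comparison, although the table does not state the test and no single variant fits all four columns.

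**Assumption not in the documents.** This is the correlation ρ, within PPV strata, between baseline oxygen need and log time to normalization. For exponential times log T has residual variance π²/6 = 1.645, so ρ corresponds to a log-hazard slope per SD of β = ρ√(1.645/(1 − ρ²)). For example, ρ = 0.5 gives β = 0.5 × √(1.645/0.75) = 0.74.

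**Simulation.** The conditional time ratio is held at 0.8, with 110 v 220 patients, a Cox model stratified by PPV, censoring at 60 days and two-sided alpha 0.2. There are 1,000 trials per setting, so each power figure carries a simulation error of about √(0.72 × 0.28/1000) = 1.4 points.

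| Assumed ρ | Strata only | With covariate |
|---|---|---|
| 0 | 72% | 72% |
| 0.2 | 70% | 75% |
| 0.3 | 66% | 72% |
| 0.4 | 61% | 73% |
| 0.5 | 56% | 73% |

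A repeat with 3,000 trials per setting (40% on PPV) gives 73 v 73, 69 v 73, 67 v 73, 61 v 72 and 55 v 72%.

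**Where the gain comes from.** At ρ = 0.5 the mean log hazard ratio (event scale) is 0.167 strata-only and 0.227 adjusted. The standard errors are 0.119 and 0.120.

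- Strata only: 0.167/0.119 = 1.403; Φ(1.403 − 1.2816) = Φ(0.122) = 55%
- Adjusted: 0.227/0.120 = 1.892; Φ(1.892 − 1.2816) = Φ(0.610) = 73%
- 95% half-widths on the log scale: 1.96 × 0.119 = 0.233 and 1.96 × 0.120 = 0.235

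The estimate moves and the width does not.

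**The other anchoring.** If the planned 0.8 is taken as the strata-only ratio, the conditional effect is larger and adjustment lifts power above plan. With 30% on PPV, adjusted power is 72% if the covariate is not prognostic, 73–74% at a hazard ratio of 0.78 per SD, and about 81% at 0.61 per SD. The two anchorings are different scenarios and should not be mixed.

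**The case against.** A reader might infer that adjustment would sharpen the primary estimate, with a variance cut by the factor 1 − ρ² and a correspondingly narrower interval. That rule belongs to linear analysis of covariance. In the Cox model the standard error stays at about 0.12, so this reading fails. Nor does adjustment alter the Kaplan-Meier medians, which are what Section 6.4.1 lists.

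A reader might also infer that the plan ignores baseline oxygen need. It does not: "Patients will be stratified by country, PPV versus supplemental O₂ at randomization, and suspected or confirmed bacterial" pneumonia. Only the gradient within the PPV and supplemental-O₂ groups is unused.

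The remaining objections are fair:

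- The strata-level and covariate-conditional hazard ratios are different quantities, and preferring the former is legitimate. The plan is not invalid.
- Section 6 rules out formal hypothesis testing, and alpha 0.2 serves planning only. That lowers the weight of a power argument. But Section 6.1 gives effect-size estimation as the purpose, and attenuation acts on the estimate.
- The prognostic strength is unknown, and at zero the gain is nil.
- The measures are not uniform. Flow is listed only for patients on supplementation, and Appendix 11 converts saturation to PaO₂, not flow to FiO₂. Appendix 1a qualifies the daily recording where clinically contraindicated. FiO₂ is, however, named for both groups.
- Section 6 defers further detail to an SAP whose text is not in the part reviewed. Covariates may be named there.

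These points limit the claim but do not remove it. The covariate costs essentially nothing in power if it proves uninformative, and the strata-only ratio can still be reported.

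**Conclusion.** The concern holds in a limited form. As written, Section 6.4 gives the primary Cox model no covariate and leaves the finer pre-dose oxygen requirement unused. If that requirement predicts recovery within strata, the strata-only hazard ratio is attenuated relative to the conditional one. The resulting power loss ranges from nothing at ρ = 0, through about 5 or 6 points at ρ = 0.2–0.3, to about 12 at 0.4 and 17 at 0.5.

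These figures assume exponential times, a conditional ratio of 0.8, pooled active versus placebo, stratification by PPV alone, and a range of ρ that the documents neither give nor bound. They also assume that the strata in the model are the randomization factors, which Section 6.4 does not state. This is a worthwhile, inexpensive improvement to the analysis, not the correction of an error.

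**What to change.** Before any unblinded interim or final analysis, state in Section 6.4 or the SAP that:

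1. The stratified Cox model for the primary endpoint (each dose and the combined doses versus placebo) uses the randomization factors as strata and adds the last pre-dose oxygen requirement as a covariate.
2. The covariate is, for example, FiO₂, with flow converted by a fixed, pre-specified table, or separate terms within the PPV and supplemental-O₂ strata.
3. A simple rule covers a missing baseline value, so that no randomized, confirmed-infected patient drops out of the analysis. Section 6.4 currently allows no imputation beyond censoring and needs an exception for this.
4. The strata-only hazard ratio is reported alongside the adjusted one, and each is labelled for what it estimates.

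The timing matters because Section 6.10 allows up to two interim efficacy analyses with the Sponsor study team unblinded at treatment-group level.

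The cost is wording, a conversion table or second term, and the missing-value rule. No new data are collected. The one substantive consequence is that the adjusted hazard ratio is conditional on baseline oxygen need and must be described that way.

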Influenza A is a membrane-enveloped RNA virus that causes significant morbidity and mortality. Currently, there is a great need in hospitalized influenza patients for a parenteral therapeutic option that is well tolerated, can rapidly resolve influenza-related signs and symptoms, decrease mortality, reduce hospital and intensive care unit (ICU) stays, as well as have a prolonged window for initiation of treatment beyond the current standard of care (i.e., within 48 hours of the onset of flu symptoms).

Approximately 200,000 to 278,000 patients are hospitalized with severe influenza infections annually in the United States (US) (Thompson et al. 2004; Zhou et al. 2012), and assuming the same rate reported in the US, an estimated 319,000 to 445,000 patients are hospitalized in the European Union (EU). Hospitalization due to severe influenza is associated with high mortality (4%–8%), ICU admission (5%–17%; Lee and Ison 2012), mechanical ventilation support in an ICU setting (7%–11%; Doshi et al. 2011), and prolonged hospital stays (5–9 days; Lee and Ison 2012). During a pandemic season, the outcomes may be more serious, with up to 34% of patients requiring ICU care and a mortality rate as high as 15% (Lee and Ison 2012).

Influenza infection is an upper and lower respiratory disease with a broad spectrum of presentations that can result in fever, shortness-of-breath, pneumonia, respiratory failure, secondary respiratory infections, and even death. The standard of care therapy for patients hospitalized with influenza consists of supportive measures and administration of available antiviral agents, primarily neuraminidase inhibitors (NAI) that include but are not limited to oseltamivir, zanamivir, *laninamivir*, and peramivir. However, a significant unmet medical need still exists in the severely ill patient population, as evidenced by the considerable degree of morbidity and mortality in this setting. To address this need, the Sponsor is developing a highly-specific anti-influenza A (MHAA4549A) antibody therapy for treatment of hospitalized patients with severe influenza.

1.2 **BACKGROUND ON MHAA4549A**

1.2.1 **Nonclinical Background**

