3.2.2 Rationale for Patient Population and Primary Endpoint

Severe influenza, for the purpose of this study, is defined as requiring one of the following treatments: any supplemental O₂ to maintain an SpO₂ > 92% or PPV. PPV is

defined as any mechanical positive pressure device to maintain oxygenation; this can include positive pressure mask and intubation.

This patient population was chosen based on the rationale that respiratory failure is a hallmark of influenza and a major driver of morbidity and mortality, as well as hospitalization. The recovery from ventilator support has been shown to be directly proportional to time spent in the ICU (Blackwood et al. 2011; Premier Inc, Charlotte, NC). Based upon an analysis of morbidity and mortality, the patient population that requires supplemental O₂ or ventilation on their first day of admission was determined to have a high unmet medical need as they have an estimated mortality of 9%-32%, and 27% require admission to the ICU, according to analysis of a database of over 70,000 hospitalized patients in the U.S. from 2005-2012 (Premier Inc, Charlotte, NC).

The proposed primary efficacy outcome measure in this study is “Time to normalization of respiratory function,” defined as oxygen saturation \geq 95% without oxygen supplementation. Support for use of a respiratory endpoint in this population comes from recently published data demonstrating that a composite endpoint that captured respiratory rate, fever, heart rate, and blood pressure resolution was primarily driven by the respiratory component of the endpoint (Marty et al. 2014). Given that influenza infections generally do not cause systemic infections and influenza disease is restricted to the respiratory tract, the Sponsor believes that the primary endpoint represents a clinically meaningful outcome in this patient population (as shown by analysis of PREMIER database) and measures an important physiologically relevant pharmacodynamic response parameter of MHAA4549A. This endpoint is a measure of patient function, measures a symptom that represents a serious consequence of influenza, and is consistent with clinically relevant endpoints discussed in the US Food and Drug Administration (FDA) Guidance, “Influenza: Developing Drugs for Treatment and/or Prophylaxis” (FDA 2011).

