3.3.2 Primary Efficacy Outcome Measures

The primary efficacy outcome measure for this study *is* as follows:

- Time to normalization of respiratory function defined as:
 - The time to cessation of O₂ support resulting in a stable SpO₂ ≥ 95% (see [Appendix 2](#) for details)

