6.4.2 Secondary Efficacy Endpoints

- *Clinical status at Days 1-7, 14, and 30 categorizing proportion of patients in each of the 6 pre-defined categories*
- Proportion of patients with clinical failure after 24 hours post-infusion of study drug
- Median time to clinical resolution of vital signs
- Hazard ratio for mortality at Day 14, Day 30, and Day 60
- Mean and median AUC of viral load

- Mean and median peak viral load
- Median duration of viral shedding in nasopharyngeal samples
- *Proportion of patients with detectable infection*
- Median duration of hospitalization
- Median duration of ICU stay
- Proportion of patients requiring antibiotics for respiratory indications during study
- Proportion of patients with influenza secondary complications
- Median duration of ventilation
- Proportion of patients who are readmitted by Day 30 and Day 60

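### Section 6.4 has no rule for death before normalization; if deaths are censored, the primary recovery curve is inflated and its hazard ratio does not register a mortality difference

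*Combined protocol and SAP*

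**What the plan says.** Section 3.3.2 of the Version 7 protocol defines the primary outcome as "The time to cessation of O₂ support resulting in a stable SpO₂ ≥ 95" percent, and Section 6.4.1 lists the endpoint as "Median time to normalization of respiratory function". Neither these sections nor Appendix 2 mentions death.

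Section 6.4 analyses time-to-event data "using Kaplan-Meier methodology and stratified Cox proportional hazards models and will be summarized using n, median when estimable, hazard ratios, and 95% confidence intervals". The censoring rule is "Patients who are lost to follow-up (while event free) will be censored at the time that they are last known to be event free", and the section closes with "Other than censoring in the time to event analyses, no other imputation for missing data will be performed". It names no competing-risk method, no worst-outcome rule and no sensitivity analysis for deaths.

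On mortality, Section 3.2.2 says of patients needing oxygen or ventilation on their first day of admission that "they have an estimated mortality of 9%-32%, and 27% require admission to the ICU", from a US hospital database. Section 1.1 cites 4% to 8% for hospitalized severe influenza. Section 4.1.2 excludes patients whom the investigator judges likely to die within 48 hours.

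Death does enter other endpoints: all-cause mortality at Days 14, 30 and 60, clinical failure, and the worst category of the ordinal clinical status (Sections 3.3.3 and 6.4.2). Section 6 defers further analysis detail to a separate SAP, which is not in the supplied text.

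**The concern.** A patient who dies on oxygen can never have the primary event. With censoring as the only mechanism offered, a programmer would most naturally censor that patient at death. Kaplan-Meier then redistributes the patient's weight to those still at risk, as though recovery had merely not yet been observed. Two things follow.

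- The estimated proportion recovered is too high and the median too short, because they describe a population in which nobody dies.
- The Cox ratio compares recovery rates only among patients still alive and on oxygen. An arm can lose more patients to death and show no deficit on the primary endpoint.

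The trial enrolls patients on oxygen or positive pressure ventilation, the latter up to about 45% of the total (Section 3.1.1), so deaths before normalization are not a remote case.

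**Working it through.** **The plan's own figure.** Section 6.1, Table 7 gives 71.4% power for medians of 4 versus 5 days in both active arms, two-sided alpha 0.20, 330 evaluable patients, exponential times and 60 days of follow-up. The probability of recovery by Day 60 at a 5-day median is 1 − 2^(−60/5) = 1 − 2^(−12) = 99.98%, so about 330 events are assumed and no deaths. Freedman's formula for pooled active versus control (2:1), with recovery ratio 5/4 = 1.25, gives:

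√(330 × 2) × 0.25 / (1 + 2 × 1.25) − 1.2816 = 1.835 − 1.2816 = 0.553, so power is 71.0%.

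That reproduces the first column. (The other three columns agree better with a 2-df log-rank test, which does not affect this point.) Table 7's ratio of 0.8 is a ratio of medians. Ratios below are recovery hazards, active over control, so values under 1 mean worse recovery.

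**Effect on the curve.** Inputs: control recovery hazard λ = ln 2 / 5 = 0.1386 per day, from the 5-day median in Section 6.1; d is the proportion dying before normalization. Constant hazards are my assumption.

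- Death hazard: λ × d / (1 − d). Total hazard: λ / (1 − d).
- Deaths censored: 1 − KM(t) = 1 − exp(−λt). The median is 5.0 days and Day-60 recovery 99.98%, for any d.
- Death competing: CIF(t) = (1 − d) × [1 − exp(−λt / (1 − d))]. The median is −ln(1 − 0.5 / (1 − d)) × (1 − d) / λ.

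| d | Total hazard | Median, death competing | Recovered by Day 60 |
|---|---|---|---|
| 4% | 0.1444 | 5.09 days | 96% |
| 8% | 0.1507 | 5.20 days | 92% |
| 9% | 0.1523 | 5.23 days | 91% |
| 20% | 0.1733 | 5.66 days | 80% |
| 32% | 0.2039 | 6.52 days | 68% |

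Worked line for 32%: 0.5 / 0.68 = 0.7353; −ln(0.2647) = 1.329; 1.329 / 0.2039 = 6.52.

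Recovery events also fall, from 330 to about 300 at 9% and 224 at 32%. The 71.0% becomes 68.0% and 59.2% by the same formula.

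**Effect on the hazard ratio.** Take a 20% control death share, so the death hazard is 0.25λ. Let the drug double it to 0.5λ and leave recovery unchanged. The active death share is 0.5 / 1.5 = 33%, and the proportion ever normalizing falls from 80% to 67%. In 2,000 simulated trials of 110 versus 220:

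- deaths censored: ratio near 1.00, with the 80% interval wholly on the harm side in 10% of trials, which is the chance rate;
- deaths kept as never normalized: ratio about 0.76 to 0.77, with harm shown in about 74% to 76%.

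At the 95% intervals that Section 6.4 specifies, the detection rates are about 3% and 50%.

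**If deaths fall on slow recoverers.** As an illustration, let 30% of patients have a 20-day recovery median and carry all the deaths, the rest a 4-day median, with about 9% versus 18% dying before normalization. The censored ratio is then 1.08, favoring the more lethal arm, against 0.87 with deaths kept as never normalized.

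**The case against.** The strongest reply is that the trial does not depend on the primary endpoint to detect deaths. In the doubled-hazard case above, a simulated comparison of mortality itself shows harm in about 92% of trials at the 80% level and 74% at the 95% level, better than the repaired primary analysis. The IMC and SOC review unblinded safety data and may recommend stopping enrollment. This stands: a reader might infer that harm could go unseen in the trial, and the documents do not support that. The blind spot is in the primary result. The mortality comparison is not a complete safeguard either: 9% versus 18% with 110 per arm has about 50% power at two-sided 0.05.

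Second, the censoring sentence names only patients lost to follow-up, and a recorded death is not loss to follow-up. A reader might infer that the protocol prescribes censoring at death; it does not. The defect is a missing rule whose natural default is censoring, and the separate SAP may supply one.

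Third, 9% to 32% is not what the protocol expects in this trial. It is a database estimate used to justify the population, Section 1.1 cites a lower range, and likely early deaths are excluded. At 4% to 8% the median moves by only 0.09 to 0.20 days, against a planned effect of 1 day.

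Fourth, the cause-specific ratio is a legitimate measure of recovery rate, and Section 6 disclaims formal hypothesis testing. Both are true. But the stated purpose is estimation, and the median and recovery curve are the estimates that go wrong.

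**Conclusion.** The point holds as a missing rule with a consequential default. If deaths are censored, the primary median is understated by about 0.1 to 0.2 days at 4% to 8% mortality before normalization, and by about 0.2 to 1.5 days at 9% to 32%. Day-60 recovery is overstated by 4 to 8 and by 9 to 32 percentage points respectively. The primary hazard ratio would show little or nothing of a mortality difference.

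These sizes rest on constant hazards, on the 5-day control median, and on reading cited mortality as death before normalization. Some deaths may follow normalization, so the competing share could be lower.

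Two further readings go beyond the text. A reader might say the trial would report recovery for patients who died; a censored patient is never counted as an event, and what is inflated is the curve. A reader might also infer that an early death would score as a short, favorable stay under "Median duration of hospitalization" and the ICU and ventilation medians. The protocol does not say how deaths enter those summaries, so that is not established.

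**What to change.** In Section 6.4, and in the SAP, state that patients who die before normalization are kept as not normalized through Day 60 and are not censored at death. Patients lost to follow-up alive remain censored as now. Report, by arm:

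- cumulative incidence of normalization with death as a competing event, giving the median and the Day-60 proportion;
- the corresponding subdistribution hazard ratio with its interval;
- the cause-specific Cox ratio beside it.

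The three duration endpoints can stay as they are. Days alive and free of hospital, ICU or ventilation may be added as a supplementary summary.

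The cost is a short text change and some programming; follow-up and mortality already run to Day 60. The drawback is that the subdistribution ratio mixes recovery and survival, which is why the cause-specific ratio belongs next to it. The rule should be fixed before any unblinded efficacy look. The IMC biostatistician and programmer see treatment assignments and also work on study conduct (Section 3.1.2), so a rule left open could be chosen by people who know the deaths by arm.
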